7.1 Standard descriptive statistics

The data of continuous type will be presented with following statistics: n (the number of subjects with no missing data), mean, median, standard deviation (SD), interquartile range (IQR), minimum and maximum values. In quantitative tests the values less than LLoQ will be replaced to 1/2 of LLoQ, the values more than ULoQ will be replaced to ULoQ.

The data of categorical type (including clinical evaluations) will be presented with n (the number of subjects with no missing data), frequencies and percentages. Unless otherwise specified, percentages by categories will be based on the number of subjects with no missing data.

The number of decimals for each descriptive statistical value will be determined by the following rules:

- mean, median and IQR: +1 decimal symbol compared to the analyzed variable values;
- standard deviation: +2 decimal symbols compared to the analyzed variable values;
- minimum and maximum values: the same as for the analyzed variable values;
- percentages will be rounded to one decimal symbol;
- confidence intervals will be presented with accuracy of the estimated value.

7.2 Statistical tests and common calculations

The following arrangements will be applied:

- all tests will be two-sided with the default significant level 5%;
- confidence intervals will be 95% and will be determined using the Clopper-Pearson method;
- type I error values (p-values) will be rounded to four decimal symbols.

For quantitative measurements of clinical laboratory data, changes from baseline will be calculated as (measurement at visit X – measurement at baseline).

7.3 Missing data

If the information about adverse event start date and time is missing or incomplete, the following rules will be used for the classification of AEs for AEs of the study period and AEs, which occurred before the start of treatment:

Table 7.1 – AEs missing management.

| Day | Month | Year | Processing |
|------------|--------------|-------------|--|
| is missing | is known | is known | AE will be classified as AE of the study period, if month and year \geq month and year of the first study drug administration date |
| is missing | is missing | is known | AE will be classified as AE of the study period, if year \geq year of the first study drug administration date |
| is known | is known | is missing | AE will be classified as AE of the study period |
| is missing | is missing | is missing | AE will be classified as AE of the study period |

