4.3 Planned analyses

The only final statistical analysis report will be performed for this study.

No analyses for DMC meetings and no interim analysis are planned in the study.

5 General considerations

Study Day will be calculated from the reference start date, and will be used to show start/stop day of assessments and events.

Reference start date is defined as the day of the start treatment (“EXSTDTC” variable from “EX” domain of the database).

If the date of the event is on or after the reference date then

study day = (date of event – reference date) + 1.

If the date of the event is prior to the reference date then

study day = (date of event – reference date) – 1.

Baseline is defined as the measurement taken on Visit 1.

6 Analysis populations

The target population (TP) – all patients with signed written Patient Authorization, who fulfill the eligibility criteria. Patients who prematurely discontinue earlier than ≤study day 55 will be used in analyses on the target population with actual EoT time point without windowing conventions adjustment for EoT.

The core population (CP) – all patients of the TP, who have started and received the treatment combination recommended in the current local label for their disease characteristics. Patients with EoT ≤ study day 55 (less than 8 weeks) will be excluded from the CP (these patients will be included to the NCP).

The safety population (SP) – all patients who received at least one dose of the ABBVIE REGIMEN.

The non-core population (NCP) – patients not receiving the treatment recommended in the local label.

The core population with sufficient follow-up data (CPSFU) – all CP patients, who fulfill one of the following criteria:

- evaluable HCV RNA data within the SVR12 time window;

¹ This section is based on the section 9.1.1 “Study Size” of clinical study Protocol.

P16-253 (CITRIN) _ STATISTICAL ANALYSIS PLAN _ FINAL 2.0 _ 16 Mar 2018

- a HCV RNA value ≥ 50 IU/mL at the last measurement post-baseline (i.e. no virological response achieved at the last measurement on-treatment or post-treatment);
- HCV RNA <50 IU/mL at the last measurement post-baseline, but no HCV RNA measurement on the SVR12 visit due to reasons related to safety (e.g. dropped out due to AE) or incomplete efficacy information (e.g. virologic failure such as relapse is reported in the eCRF but date and value of the corresponding HCV RNA test is missing).

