10.2 Adverse events

Only treatment-emergent adverse events will be analyzed.

Treatment-emergent AE is any reported event that begins or worsens in severity after initiation of study drug through 30 days post-study drug dosing.

All analyzed AEs will be coded using the MedDRA version 20.0 (or further updating) and tabulated in the report with grouping by primary system organ class (SOC) and preferred term (PT).

The frequency of a specific AE occurrence will be presented by the proportion of patients with this AE emergence as well as the total number of episodes this AE for a diagnosis.

The following tables with descriptive statistics in accordance with section 7.1 will be presented:

- all AE / SAE;
- AE / SAE by severity;
- AE / SAE by relationship to the study drug.

Tables of AE/SAE by severity (relationship to the study drug) will be prepared using the following rules. Each SOC / PT category will include only the AEs with the highest severity (relationship to the drug) in each patient, while in the Total category all AEs of this patient will be considered. At the same time, each patient will be counted only once with highest severity (relationship to the study drug) in each SOC and each PT level as well as Total level.

Also all AEs will be presented in listings. Additional listings for unintended medication errors will be provided.

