| Total [1] | XX (XX.X) /XX |
| System organ class 1 | XX (XX.X) /XX |
| Preferred term A | XX (XX.X) /XX |
| Preferred term B | ... |
| ... | ... |
| System organ class 2 | ... |
| ... | ... |
| ... | ... |

N: the number of patients in the safety population.

n: the number of patients who have AE with appropriate SOC/PT. Percentages are calculated as (100 x n/N).

E: the number of AE episodes, which have an appropriate SOC and/or PT.

Patients with several AEs having the same SOC and PT are accounted only once for appropriate SOC and PT.

[1] The Total line displays the number (n) and the proportion (%) of patients who have at least one AE as well as the total number of AE episodes in the study.

The coding is carried out by the dictionary MedDRA v.20.0.

The table does not include AEs that occurred prior to the first intake of the study drug.

The data is sorted alphabetically: first by SOC, then by PT.

Program code, date, time

Data extracted: DD.MM.YYYY

Similar to table 3.2.1, table 3.2.2 will be constructed:

P16-253 (CITRIN) _ STATISTICAL ANALYSIS PLAN _ FINAL 2.0 _ 16 Mar 2018**Table 3.2.2 Serious adverse events**

P16-253 (CITRIN) _ STATISTICAL ANALYSIS PLAN _ FINAL 2.0 _ 16 Mar 2018

AbbVie LLC

P16-253 (CITRIN)

Table 3.2.3 Adverse events by relationship to the study drug

The safety population

Page X of X

| System Organ Class (SOC) Preferred term (PT) | Relationship to the study drug | Total (N=XX) n (%) /E |
|---|--|---|
| Total [1] | Reasonable possibility No reasonable possibility Total | XX (XX.X) /XX XX (XX.X) /XX XX (XX.X) /XX |
| System Organ Class 1 | Reasonable possibility No reasonable possibility Total | XX (XX.X) /XX XX (XX.X) /XX XX (XX.X) /XX |
| Preferred term A | Reasonable possibility No reasonable possibility Total | XX (XX.X) /XX XX (XX.X) /XX XX (XX.X) /XX |
| Preferred term B | Reasonable possibility ... | XX (XX.X) /XX ... |
| System Organ Class 2 | Reasonable possibility ... | XX (XX.X) /XX ... |

N: the number of patients in the safety population.

n: the number of patients who have AE with appropriate SOC/PT. Percentages are calculated as (100 x n/N).

E: the number of AE episodes, which have an appropriate SOC and/or PT.

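### SAP Table 7.1 ignores the AE stop date, so an event that ended before first dose can be classed as a study-period AE

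*SAP*

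**What the plan says.** SAP 7.3 introduces Table 7.1 as a rule for the "classification of AEs for AEs of the study period and AEs, which occurred before the start of treatment". It is a two-way split with four rows:

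- Day missing, month and year known: "AE will be classified as AE of the study period, if month and year" are at or after those of first dose.
- Only the year known: "AE will be classified as AE of the study period, if year" is at or after that of first dose.
- Day and month known, year missing: always study-period.
- Everything missing: always study-period.

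No row refers to the stop date.

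SAP 10.2 states that "Only treatment-emergent adverse events will be analyzed", and defines such an event as one that "begins or worsens in severity after initiation of study drug through 30 days post-study drug dosing". The footnote to shell Table 3.2.1 (SAP section 18) says "The table does not include AEs that occurred prior to the first intake of the study drug"; it does not mention the 30-day limit. SAP section 5 says that Study Day "will be used to show start/stop day of assessments and events".

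**The concern.** An event that has ended before first dose can neither begin nor worsen after it, so under 10.2 it is not treatment-emergent. Table 7.1 is the only stated rule for placing an AE with an incomplete start date before or after first dose, and it disregards the one other date that could settle the matter. A programmer who follows it literally would count some events that the recorded data show to be pre-treatment. Tolerability is a secondary objective, and the AE tables are its main output.

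A smaller point concerns the other end of the window. The 30-day limit appears in 10.2 but not in Table 7.1 or the AE table footnotes, and the SAP does not say in which order the two rules apply.

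**Working it through.** The plan gives no figure to reproduce. The check applies Table 7.1 literally to dated examples and compares the result with 10.2.

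**Inputs**
- AE collection starts at patient authorization (Protocol 11.1.4).
- First dose is planned no later than 2 weeks after enrollment (Protocol 9.6), so the pre-dose interval is at most about 14 days. Patients enrolled after starting treatment have none.
- Treatment lasts 12 weeks, taken as 84 days of dosing. Follow-up is up to 12 weeks, or 84 days, after treatment (SAP 4.1).
- Planned size is 60 patients (Protocol 9.11).
- Assumption: an AE stop date is recorded.

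**Lower limit, example.** First dose 20 March 2017; the AE stopped on 12 March 2017, which is 20 − 12 = 8 days earlier. Under 10.2 it is not treatment-emergent. Table 7.1 gives:
- start March 2017: study-period (wrong)
- start 2017 only: study-period (wrong)
- start wholly missing: study-period (wrong)
- start February 2017: pre-treatment (right)

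**How often the start date alone fails to show a pre-dose onset.** An onset k days before first dose falls in the same calendar month if first dose is on day k + 1 of the month or later. In a 30-day month with all dosing days equally likely, that share is (30 − k)/30. Averaged over k = 1 to 14 it is 1 − 7.5/30 = 75%. Enumerating first doses from 10 March to 24 September 2017 (start of data collection, plus about 6 months of enrollment, plus 2 weeks) gives 77% with the day missing. It gives 100% with only the year known, because every such onset is in 2017. Both figures assume onset is uniform over the 14 days. They describe all pre-dose onsets with a partial date; only those that also ended before first dose are provably misclassified.

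**Upper limit, same patient.** Last dose is 20 March + 83 days = 11 June 2017, and the 30-day limit is 11 July 2017.
- Start July 2017: could be 1 July, inside the window, so it is ambiguous.
- Start August 2017: earliest date 1 August, 21 days past the limit.
- Start September 2017: earliest date 1 September, 52 days past the limit.

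Table 7.1 calls all three study-period, but August and September fail 10.2 whatever the day. In the enumeration, for onsets 31 to 84 days after last dose, the month alone proves the event too late in 71% of cases.

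**Size.** One extra patient in a row adds at most 1/60 = 1.7 percentage points. Section 10.2 counts each patient once per PT, SOC and total, so a patient already in the row adds nothing.

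**The case against.** The strongest reply is that Table 7.1 makes a first split only and that 10.2 and the shell footnote do the rest. At the upper end this largely stands. A reader might infer that events starting well after the 30-day limit will enter the AE tables. The documents do not support that: Table 7.1 only separates pre-treatment events from later ones, nothing in 7.3 exempts an event from 10.2, and a start month wholly after the limit fails 10.2 without a day being needed. Protocol 11.1.4 also ends AE collection at 30 days, although the SVR12 visit lists still record AEs. What remains is a missing statement of the order of the rules.

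At the lower end the reply is weaker. For incomplete dates, Table 7.1 is the SAP's own test of whether an event preceded treatment, so 10.2 and the footnote depend on its answer and do not check it independently.

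Other objections stand as limits. The AE page of the eCRF is not shown, and section 5 only implies a stop date. The pre-dose interval is short, and the event must begin and end within it. Data queries may complete many dates. Inclusive assignment of uncertain events is a reasonable, cautious choice. It might also be inferred that partial dates cluster among events recalled at the SVR12 visit, but the documents contain nothing on that.

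**Conclusion.** The point holds for the lower limit: Table 7.1 can class as study-period an AE that its recorded stop date shows to be pre-treatment, contrary to 10.2. This needs a partial start in the month or year of first dose, or a missing year; a known earlier month is handled correctly while the year is known. For the upper limit, the SAP needs a clarification only.

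The matter is minor. The documents give no rate of partial dates, and few events are likely to be affected. The ceiling is 1.7 points per patient per row with 60 patients in the safety population, reached only when that patient has no other event in the row. The conclusion assumes that AE stop dates are recorded. SVR12 is not touched.

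**What to change.** Add one condition to Table 7.1: an AE with a partial or missing start date is pre-treatment if its stop date, where recorded, is before first dose. Otherwise keep the inclusive rule.

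For consistency, state in 7.3 or 10.2 that AEs passing Table 7.1 remain subject to the 10.2 upper limit, so that an AE whose earliest possible start is later than last dose + 30 days is not tabulated as treatment-emergent. Add the same limit to the AE table footnotes. Ambiguous events, such as the July example, stay in.

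The cost is two sentences in the SAP, the footnotes, and two conditions in the AE derivation. No new data are needed if stop dates are already held.

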7.4 Multicenter studies

The study will take place in 5-7 centers (national and regional hospitals/outpatient services). Data from all centers will be merged and analyzed as one population for all study endpoints.

7.5 Multiple comparisons

No adjustments for multiplicity are required.

8 Summary of study data

Each study variable will be analyzed for relevant population.

Unless otherwise specified all raw data will be listed and sorted by unique subject identifier and study period/assessment (i.e. time point), where applicable.

Demographic and baseline characteristics, concurrent illnesses and medical conditions, prior and concurrent medications will be reported for *the core population (CP)*.

The results will be presented overall and for the CP analysis groups based on genotype 1 subtype, fibrosis status and treatment experienced or naïve.

According to the eligibility criteria of this study¹, only patients with genotype 1b and Child Pugh A cirrhosis will be included in this study. In this way, the results will be presented for the CP analysis groups by the following parameters:

- cirrhosis score² (5 or 6);

- treatment experienced or naïve patients³ (with/without prior treatment for CHC).

Additionally demographic and baseline characteristics, concurrent illnesses and medical conditions, prior and concurrent medications will be reported for *the target population (TP)* and *the safety population (SP)* overall only (without the CP analysis grouping).

8.1 Subject disposition

Subject disposition will be represented in tables and listings for *all patients who signed the written patient authorization form* and will include the following results:

- the number of subjects who signed the written patient authorization form;
- the number of subjects in each analyzed population;
- the number of subjects who has HCV RNA assessment on SVR12;
- the number of subjects without HCV RNA assessment on SVR12 and the reasons for it;
- the number of patients with the violations of the eligibility criteria and the corresponding violated inclusion/exclusion criteria.

8.2 Protocol deviations

The presentation of Protocol deviations is not planned in this study.

8.3 Demographic and baseline variables

Tables with descriptive statistics in accordance with section 7.1 will be presented for the following parameters, which are evaluated on visit 1:

- demographics and anthropometric characteristics:
 - gender;
 - race/ethnic origin;
 - height;
 - weight;
 - BMI [weight (kg) / height (m²)];
 - duration of HCV infection diagnosis (in years);
 - IL28B genotypes;

¹ Sections 9.6 "Inclusion Criteria" and 9.7 "Exclusion Criteria" of the clinical study Protocol.

² Parameter "CIRRHOSIS SCORE" from eCRF form "CHC DISEASE CHARACTERISTICS".

³ Parameter "Prior treatment for CHC" from eCRF form "MOST RECENT PRIOR THERAPY FOR CHC".

P16-253 (CITRIN) _ STATISTICAL ANALYSIS PLAN _ FINAL 2.0 _ 16 Mar 2018

- most likely mode of HCV infection;
- liver biopsy results (staging by histopathological scoring system):
 - elastography (kPa);
 - FibroTest;
- presence of esophageal varices;
- history of liver decompensation;
- Child Pugh score;
- alcohol consumption:
 - alcohol use;
 - number of units/drinks per week (for patients who regular use alcohol).

All corresponding listings will be presented.

8.4 Concurrent illnesses and medical conditions

Medical history will be coded using the MedDRA version 20.0 (or further updating) and summarized by system organ class (SOC) and preferred term (PT) according Data MATRIX LLC SOP [3] and will be presented in listings and tables.

Tables with descriptive statistics in accordance with section 7.1 will be presented for the following parameters, which are evaluated on visit 1:

- co-infection information:
 - presence of co-infection with other relevant diseases;
 - CD4 T-cell count (for HIV co-infected patients);
 - HIV-RNA test results (for HIV co-infected patients);
- liver and/or CHC related co-morbidities;
- other co-morbidities.

8.5 Prior and concurrent medications

All medications will be coded using WHODD version Jun 2015 (or actual version on the time of the study completion) according Data MATRIX LLC SOP [3]. Prior and concurrent medications will be presented in a separate listings and tables.

Prior medication will be determined using “MOST RECENT PRIOR THERAPY FOR CHC” flag in the CMCAT variable of CM domain of the database. Concurrent medications will be determined using “CO-MEDICATION” flag in the CMCAT variable of CM domain of the database.

Additionally listings will contain the following information for prior CHC therapy:

- presence of prior treatment for CHC;
- generic drug name;
- initial dose (by generic drug name groups and units groups);
- start frequency (by generic drug name groups);
- duration (by generic drug name groups, in weeks);
- outcome prior treatment.

9 Effectiveness analysis

All analyses of effectiveness will be performed on the TP, CP and CPSFU populations with separate tables for each population as the result. Tables for equal sets (contain exactly the

P16-253 (CITRIN) _ STATISTICAL ANALYSIS PLAN _ FINAL 2.0 _ 16 Mar 2018

same patients) will not be presented, equal sets will be pointed in the footnote with description only.

The following effectiveness outcomes will be included in the analyses:

- SVR12 achieving;
- virological response at EoT;
- patients with at least one and each of SVR12 non-response categories:
 - relapse during treatment phase;
 - relapse after EoT;
 - failure to suppress;
 - premature study drug discontinuation with no on-treatment virologic failure;
 - missing SVR12 data.

Due to the fact that in the Russian clinical practice tests for HCV RNA often have limit of detection higher than 50 IU/mL and may vary across laboratories, effectiveness outcomes will be analyzed with the following definitions:

- SVR12 achieving (single last HCV RNA value <50 IU/mL or undetectable/negative 12 weeks after the last actual dose of the ABBVIE REGIMEN);
- virological response (HCV RNA <50 IU/mL or undetectable/negative) at EoT;
- patients with at least one and each of SVR12 non-response categories:
 - relapse during treatment phase (breakthrough, i.e. at least one documented HCV RNA value <50 IU/mL or undetectable/negative followed by HCV RNA value \geq 50 IU/mL or positive during treatment);
 - relapse after EoT (HCV RNA value <50 IU/mL or undetectable/negative at EoT or at the last on-treatment HCV RNA measurement followed by HCV RNA \geq 50 IU/mL or positive post-treatment);
 - failure to suppress (each measured on-treatment HCV RNA value \geq 50 IU/mL or positive);
 - premature study drug discontinuation with no on-treatment virologic failure;
 - missing SVR12 data and/or none of the above criteria.

Figure 9.1 illustrates the patient's distribution by SVR12 response/non-response categories.

P16-253 (CITRIN) _ STATISTICAL ANALYSIS PLAN _ FINAL 2.0 _ 16 Mar 2018

[figure not shown]

Figure 9.1 – Patient's distribution by SVR12 response/non-response categories. Frequencies and percentages with 95% confidence intervals will be calculated for each effectiveness outcomes and will be presented according the section 7.1. Also frequency tables will be repeated for patients in subgroup without missing SVR12 data category.

Effectiveness endpoints (SVR12 achieving, virological response at EoT and relapse after EoT) will be analyzed using univariate logistic regression, if applicable. These analyses will be of exploratory nature, data driven, and will be repeatedly performed for various CP analysis groups, since not each covariate might be predictive in each patient group.

The following parameters can be included in the univariate models as explanatory variables (fixed effect or covariate):

- treatment experience (with/without prior treatment for CHC);
- Child Pugh score;
- result of FibroTest;
- history of liver decompensation;
- age;
- gender;
- race;
- BMI;
- laboratory hematology¹:
 - hemoglobin;
 - platelets;
 - prothrombin time;
 - laboratory clinical chemistry:
 - ALT;

¹ Note that all Hematology variables and all Clinical Chemistry should be in the same units. If it is impossible to bring units to the same the smallest units groups will be accepted as missing. If it is impossible to identify the smallest units groups the corresponding covariate will be deleted from the analysis.

P16-253 (CITRIN) _ STATISTICAL ANALYSIS PLAN _ FINAL 2.0 _ 16 Mar 2018

- AST;
- Gamma-GT;
- total bilirubin;
- albumin;
- creatinine clearance;
- alpha-1-fetoprotein.

Additionally, after univariate model analyses all effectiveness endpoints can be analyzed using MLR (if applicable) which consider only covariates in the selection procedure with a p-value <0.25 in the corresponding univariate logistic regression analysis¹.

To avoid the multicollinearity problem all possible explanatory variables will be examined using following SAS script:

```
ods graphics on;
PROC CORR data=<dataset> plots=all;
VAR <variables>;
RUN;
ods graphics off;
```

Statistical significant correlated variables with correlation coefficient ≥ 40 should be considered and managed. All solutions about an explanatory variables choosing will be of exploratory nature, data driven, and will be described with presenting of results of the "PROC CORR" SAS procedure.

Backward selection procedures will be applied to generate the final MLR models esing the SAS procedure LOGISTIC with statement SELECTION = BACKWARD and SLENTRY = 0.05. A p-value <0.05 condition will be used for the covariates to stay in the model in a backward elimination step.

Odds ratio with 95% Wild CI, p-values will be presented for each predictor.

All data for effectiveness analyses will be listed in separate listings (for each effectiveness analyses endpoint).

10 Safety analysis

Safety analysis will be conducted on *the safety population (SP)*.

The following parameters will be analyzed:

- study drug exposure;
- adverse events;
- pregnancies;
- clinical laboratory evaluations.

